#### STUDY DESIGN AND SAMPLE SIZE

This is a prospective, open-label, Phase II study. The study will consist of a single treatment phase including:

- Screening period
- 12 weeks (90 days) of treatment period.

The planned sample size for this study is 17 subjects. In order to evaluate primary and secondary outcomes, study assessments will be conducted at Day 0, 30, 60 and 90 of treatment.

The MCID for FEV1 is 12% and 200 ml measured by spirometry obtained at baseline (immediately prior to the start of the treatment) with the results obtained 2 hour after administration of study medication (2-hour postdose FEV1) after 12 weeks of treatment.

The MCID for  $FE_{NO}$  is a reduction of at least 20% in  $FE_{NO}$  for values over 50 ppb or more than 10 ppb for values lower than 50 ppb will be used as the cut point to indicate a significant response to treatment.

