*Lignosus rhinocerus* TM02® as an immunomodulatory agent for the treatment of uncontrolled asthma: A prospective, open-label, single-arm, Phase II study.

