## Objectives

The primary objective is to assess the effect of *Lignosus rhinocerus* TM02® in reducing airway inflammation by measurement of exhaled nitric oxide ( $FE_{NO}$ ) and to assess the effect of *Lignosus rhinocerus* TM02® in bronchodilation by measurement of trough forced exhaled volume in 1 second (FEV1).

The secondary objective is to assess the effect of *Lignosus rhinocerus* TM02® to be used as complementary therapy to improve symptoms and prevent exacerbations in asthma patients as assessed by the asthma control questionnaire (ACQ-7).

The tertiary objective is to assess the safety profile of *Lignosus rhinocerus* TM02® as complementary therapy in asthma patients.

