# Endpoints

#### **Primary Endpoints**

- Change in mean trough FEV1 expressed as mililitres after 90 days of treatment
- Change in mean ACQ-7 scores after 90 days of treatment
- The threshold for change in ACQ-7 scores that is considered clinically important (MCID) is 0.5.

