#### **Study Population**

The target population for this study consists of 10 Patients with uncontrolled asthma aged 18 and above. Each subject will have to fulfil the inclusion criteria listed below. Subjects will not be included in the study if they meet any of the exclusion criteria listed below.

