#### Protocol violation

Any subject found to have entered this study in violation of the protocol will be discontinued from the study at the discretion of the principal investigator. This will include any subject found to have been inappropriately enrolled (did not meet eligibility criteria). Subject non-compliance includes either not showing up for study visits, not taking investigational product as directed, or refusing to undergo study visit procedures. Subjects who are found to be less than 75% compliant with test article usage at any study visit will be withdrawn. Subjects who are found to be taking prohibited medications or supplements without the knowledge of the principal investigator will also be withdrawn. Any major protocol deviations (i.e., those that increase the risk to subjects and/or compromise the integrity of the study or its results) will result in subject discontinuation.

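### The protocol gives two sizes for the same single-arm trial, 17 subjects and 10 patients, and nothing reconciles them

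*Protocol*

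**What the plan says.** The title describes "A prospective, open-label, single-arm, Phase II study". Under *STUDY DESIGN AND SAMPLE SIZE* the protocol describes a single treatment phase and says "The planned sample size for this study is 17 subjects". Under *Study Population*, immediately before the eligibility criteria, it says "The target population for this study consists of 10 Patients with uncontrolled asthma aged 18 and above", and adds that each subject must meet the inclusion criteria.

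Two other places bear on how many subjects will contribute data:

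- *Protocol violation* makes withdrawal compulsory for poor compliance: "Subjects who are found to be less than 75% compliant with test article usage at any study visit will be withdrawn".
- *Early Withdrawal* asks that end-of-study evaluations be done at withdrawal where possible.

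The protocol states no dropout allowance, replacement rule, staging, or separate enrolled and evaluable numbers.

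**The concern.** A single-arm trial with one treatment phase has one sample size. There is no second arm, cohort or stage to hold the other seven subjects. The two sentences therefore cannot both state the size of the trial unless they count different things, and neither says that it does.

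The number of subjects determines the precision of every mean change listed as a primary or secondary endpoint. It also determines how much the safety objective can show. A reader cannot tell when enrolment is complete. A report on 10 subjects could be called complete or 41% short (7/17); a report on 17 could be called on target or 70% over (7/10).

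A secondary risk follows. The protocol plans no stop based on results, but the trial is open-label, and ACQ-7 and FeNO are measured at Days 30, 60 and 90. With two sizes in print, ending enrolment at either could afterwards be called planned.

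**Working it through.** **Inputs from the protocol.** Size 17 (*STUDY DESIGN AND SAMPLE SIZE*); size 10 (*Study Population*); one arm (title); ACQ-7 threshold, "The threshold for change in ACQ-7 scores that is considered clinically important (MCID) is 0.5" (*Primary Endpoints*); FEV1 threshold, which "is 12% and 200 ml measured by spirometry obtained at baseline" (*STUDY DESIGN AND SAMPLE SIZE*). The protocol gives no alpha, power, SD of change or dropout rate, so neither 17 nor 10 can be reproduced. An SAP might supply those inputs, and their absence is not the point here.

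**Step 1: can dropout link the two numbers?** Enrolled = 10/(1 − d), rounded up, where d is the proportion lost.

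- d = 10%: 10/0.90 = 11.1, so 12
- d = 20%: 10/0.80 = 12.5, so 13
- d = 30%: 10/0.70 = 14.3, so 15
- d = 40%: 10/0.60 = 16.7, so 17

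The result is 17 only when 10/(1 − d) lies above 16 and at most 17, that is, for d above 1 − 10/16 = 37.5% and up to 1 − 10/17 = 41.2%. No such loss is stated.

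**Step 2: precision of a mean change.** 95% CI half-width in SD units = t(0.975, n − 1)/√n.

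- n = 17: 2.120/√17 = 0.514
- n = 10: 2.262/√10 = 0.715
- Ratio: 0.715/0.514 = 1.39

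This ratio needs no assumed SD.

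**Step 3: against the ACQ-7 threshold.** An observed mean change of exactly 0.5 has a 95% CI excluding zero only if the half-width is below 0.5.

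- n = 17: SD of change below 0.5/0.514 = 0.97
- n = 10: SD of change below 0.5/0.715 = 0.70

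**Step 4: safety.** With no events observed, the one-sided 95% upper bound on the event rate is 1 − 0.05^(1/n).

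- n = 17: 16.2%
- n = 10: 25.9%

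**Step 5: illustration of power, on assumptions.** One-sample t-test on change, two-sided alpha 0.05 (assumed). The change detectable with 80% power is 0.72 SD at 17 and 1.00 SD at 10. For the thresholds above, over a range of assumed SDs of change:

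| Change | Assumed SD | Power, n = 17 | Power, n = 10 |
|---|---|---|---|
| FEV1 200 ml | 200 ml | 97% | 80% |
| FEV1 200 ml | 250 ml | 87% | 62% |
| FEV1 200 ml | 300 ml | 73% | 47% |
| FEV1 200 ml | 400 ml | 49% | 29% |
| ACQ-7 0.5 | 0.5 | 97% | 80% |
| ACQ-7 0.5 | 0.7 | 79% | 52% |
| ACQ-7 0.5 | 0.9 | 58% | 35% |
| ACQ-7 0.5 | 1.0 | 49% | 29% |

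The contradiction does not depend on this step.

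**The case against.** The strongest reply accepts that the numbers conflict and disputes what follows from it.

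- **The numbers might be reconcilable.** A loss near 40% would connect them, so they are unreconciled rather than impossible to reconcile. True in logic, but that loss is stated nowhere, and the sentence with 10 goes on to say that each subject must meet the entry criteria. That describes people entering the trial, not completers.
- **The headings favour 17.** That figure stands under the sample-size heading, and 10 may be a leftover in the eligibility text. This is plausible but not shown, so it does not settle which number is right.
- **No precision was ever stated, so none is misstated.** Correct. The interval widths measure the consequence of the conflict; they are not a second error.
- **Withdrawal need not shrink the analysed number.** This stands in part. Withdrawn subjects may still provide end-of-study evaluations, so the compliance rule does not explain the gap. It does show why the number needs a label.
- **The stopping concern is hypothetical.** Also fair: the protocol describes no interim look. It is a side risk, and the finding does not rest on it.
- **A replacement rule and a sentence fixing the end of enrolment go beyond the error.** Reasonable; these are useful additions, not the core correction.

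An SAP could justify one of the numbers, but it could not remove a conflict between two sentences of the protocol.

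**Conclusion.** The concern holds, and the protocol must be corrected. It gives both 17 and 10 as the size of one single-arm trial, and at least one is wrong as written. The choice changes the 95% CI half-width for every mean change from 0.51 SD to 0.72 SD, and the zero-event upper bound for an adverse event from 16% to 26%. These figures assume that the stated number is the number analysed; the interval widths also assume a t-based interval for the mean change. The power figures rest in addition on an assumed alpha and assumed SDs, and serve only as illustration. The document does not show which number is correct.

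**What to change.** State one number, 17 or 10, in both *STUDY DESIGN AND SAMPLE SIZE* and *Study Population*. Say whether it counts enrolled or evaluable subjects; if these differ, give both with the assumed loss. State the precision the retained number delivers: a 95% CI half-width of 0.51 SD if 17 are analysed, or 0.72 SD if 10.

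Two short additions would help but are not essential. One says whether subjects withdrawn under *Protocol violation* are replaced. The other is a sentence such as: *Enrolment ends when this number is reached and will not be changed on the basis of accruing results.*

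The correction itself is wording and adds no visits or tests. It is free of recruitment cost only if the number chosen is the one already being recruited to. Settling on 17 when 10 was resourced means seven more subjects, and defining the number as evaluable, or replacing withdrawals, would also raise enrolment. The stated precision will look modest, and a later change of number would need an amendment.

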#### **Inclusion Criteria**

All adults aged 18 years and above with a prior documented diagnosis of atopic (Th2driven) asthma by a physician based on Global initiative for Asthma (GINA) 2020 Guidelines whose asthma is uncontrolled on ICS/LABA combination therapy based on the following criteria:

- a) A well documented requirement for regular treatment with a minimum dose of either fluticasone /salmeterol combination therapy or budeosnide/formoterol combination therapy in the 12 months prior to screening with or without maintenance of oral corticosteroids (OCS).
- b) Forced expiratory volume (FEV1) > 50% to <80% predicted normal during the screening phase (3 attempts maximum) and on the randomization day prior to the first dose of IMP.
- c) Reversibility of at least 12% and 200 ml in FEV1 after 200 ug to 400 ug (2 to 4 inhalations) of salbutamol during the screening phase (3 attempts maximum), or documented history of reversibility test that met these criteria within 12 months prior to screening.

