#### Screening includes:

- Review of medical history and concomitant therapies.
- Symptoms examination
- Phyiscial examination
- Review of inclusion/exclusion criteria
- Exhaled nitric oxide (FENO) measurements

If  $FE_{NO}$  is > 25 ppb,

- Spirometry measurement (FEV1 and FVC)
- Laboratory tests (basic hematology and chemistry)
- Urine pregnancy test for women of childbearing potential
- ECG

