#### Baseline - (Visit 1 / Week 0/ Day 0)

Subjects will receive the treatment regimen of LiGNO™ TMM.

Eligible subjects will return to the clinic in a fasted condition (last food intake at least 12 hours before the visit; subjects will be allowed to drink water) for baseline assessments:

- vitals signs, weight and height measurement
- Asthma Control Questionnaire
- review of concomitant therapies
- physical examination
- Review of spirometry measurements (FEV1 and FVC)
- Review of laboratory tests (basic hematology and chemistry)
- Review of urine pregnancy test for women of childbearing potential
- Review of baseline ECG

After all baseline assessments are reviewed, subjects will be dispensed the investigational product.

Subjects will receive LiGNO™ TMM. Subjects will be instructed in detail by site personnel about the dosing regimen. The first dose of study product is to be taken the day after the Baseline visit, treatment Day 1, consisting of :

• 2 capsules of 250 mg L. rhinocerus, once a day after breakfast and dinner daily for 4 weeks

Subjects will be given a diary card to record their symptoms every day. Subjects will be reminded to fast (12 hours) prior to their study visits. The next visit will be scheduled for Week 4/Day 30.

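### The only FEV1 MCID is defined on a 2-hour postdose reading that no visit schedules, while the primary endpoint is trough FEV1; the Day 0 baseline FEV1 is required in one place and only reviewed in another

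*Protocol*

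**What the plan says.** **Which FEV1.** The Protocol's Objectives section sets out to assess the effect "in bronchodilation by measurement of trough forced exhaled volume in 1 second". Under Primary Endpoints the first entry is "Change in mean trough FEV 1 expressed as mililitres after 90 days of treatment"; the other primary endpoint is ACQ-7. Under STUDY DESIGN AND SAMPLE SIZE, the FEV1 MCID is 12% and 200 mL, comparing a baseline taken "immediately prior to the start of the treatment) with the results obtained 2 hour after administration of study medication" after 12 weeks. That sentence also labels the later reading as 2-hour postdose FEV1. No other FEV1 MCID is given.

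**Which baseline.** The design section says that, for the primary and secondary outcomes, "study assessments will be conducted at Day 0, 30, 60 and 90 of treatment". Inclusion criterion b requires FEV1 above 50% and below 80% "predicted normal during the screening phase (3 attempts maximum) and on the randomization day prior to the first dose of IMP". The screening list contains "Spirometry measurement (FEV 1 and FVC"), a new measurement. The Day 0 list contains "Review of spirometry measurements (FEV 1 and FVC"), and the first dose follows the next day.

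**At Day 90.** The End of Treatment Visit lists one spirometry, directly after FeNO. It states no timing relative to the last dose.

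**The concern.** A threshold for clinical importance is useful only if it refers to the quantity being estimated. Here the endpoint is a trough change and the threshold is written for a postdose change. For an objective framed as bronchodilation, time since dose is part of what defines the reading. A Day 90 mean change set against 12% and 200 mL would be judged by a criterion written for a different measurement.

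The baseline is the other half of the same endpoint. If the Day 0 list is followed, the only pre-treatment FEV1 is the screening reading, which also had to fall inside an eligibility window, with up to three attempts allowed. A selected baseline pulls later readings back toward each patient's usual level. The title describes "A prospective, open-label, single-arm, Phase II study", so no control arm would separate that drift from a treatment effect. A reading not taken at Day 0 cannot be recovered at analysis, so a SAP could not repair this.

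**Working it through.** The protocol gives no figure to reproduce on this point. It states a sample size of 17 without a derivation and does not tie the 200 mL to it. The check is therefore a comparison of sections.

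**1. FEV1 named in each place**

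| Protocol section | FEV1 |
|---|---|
| Objectives | trough |
| Primary Endpoints | trough, change in mL, 90 days |
| STUDY DESIGN AND SAMPLE SIZE (MCID) | 2-hour postdose at 12 weeks against pre-treatment baseline |

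The MCID sentence gives the postdose timing both in words and as a label, so a slip of one word does not explain it.

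**2. Spirometry in the visit lists**

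| Visit | Spirometry | In-clinic dose or 2-hour wait |
|---|---|---|
| Screening | measured, if FeNO > 25 ppb | none |
| Day 0 | reviewed | none; first dose next day |
| Day 30 | not listed | none |
| Day 60 | not listed | none |
| Day 90 | measured once, after FeNO | none |

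No visit produces a 2-hour postdose value.

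**3. What the Day 90 reading probably is.** Subjects are reminded to fast for 12 hours before study visits, and from Day 30 product is taken after breakfast and after dinner. A subject who arrives fasted has not had breakfast, so the last dose should have followed the previous evening's dinner, about 12 hours or more earlier. Remaining product is handed back at that visit. The reading is thus effectively a trough, which fits the endpoint and not the MCID. This is inferred from the fasting and dosing text; the Day 90 visit does not state it.

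**4. What the baseline is.** The design section places it immediately before treatment. Criterion b requires a reading before the first dose on a randomization day; nothing is randomized in this single-arm study, and Day 0 is the nearest reading. The Day 0 list says review, whereas the screening and Day 90 lists say measurement. The schedule therefore yields one pre-treatment FEV1, at screening, and the second half of criterion b cannot be checked from it.

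**5. Effect of using the qualifying value as baseline.** The documents give none of the inputs needed, so this is an illustration of direction only. Model, with no treatment effect: true FEV1 (% predicted) ~ N(μ, 15²); each reading = true value + N(0, 6²); a patient qualifies on the first of up to three independent readings between 50 and 80; result = mean(Day 90 reading − baseline). The means, both SDs and the independence of attempts are assumptions.

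- μ = 75: about +1.5 points of % predicted.
- μ = 65, the middle of the window: (50 + 80)/2 = 65, about 0.
- μ = 55: about −1.5 points.

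The sign depends on where the screened population sits relative to the window, which the protocol does not say. If a Day 0 reading must also lie in the window, the figure at μ = 75 falls to about 0.8, whichever of the two readings is used as baseline. The second eligibility reading produces the reduction; the choice of baseline between the two does not.

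**The case against.** The strongest reply is that a site can work out what to do. The objective and the endpoint agree on trough, the Day 90 list has one spirometry with no dose beforehand, and the fast makes it a pre-dose reading in practice. Only the MCID sentence is out of line. The protocol says the FeNO MCID will serve as a cut point but gives the FEV1 MCID no such role, and no responder or success rule is attached to the FEV1 endpoint.

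Much of this stands. A reader might infer that the Day 90 timing is wholly open, or that the primary endpoint cannot be computed. The documents do not support either: the fasting and dosing text gives an approximate minimum time since dose, and a mean change in mL can be calculated without an MCID. The mismatch affects how the result is interpreted. It remains a contradiction, because the only threshold offered for that interpretation belongs to a reading the trial will not take.

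A reader might also infer that the screening baseline will inflate the apparent benefit by a calculable number of millilitres. That does not follow either. Patients with uncontrolled asthma could have a screened mean below or above 65% predicted, and the bias changes sign there.

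Finally, reading the randomization day as Day 0 is an inference. Even a Day 0 reading would precede the first dose by a day, so it only approximates the design section's timing.

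**Conclusion.** The point holds on the text. The stated FEV1 MCID does not apply to the primary endpoint as defined or as scheduled, and the Day 0 visit omits a pre-treatment FEV1 that two other sections call for. Followed as written, the schedule makes the qualifying screening value the baseline of an uncontrolled change and leaves part of criterion b unverifiable. Regression to the mean would enter that change, but its size and direction cannot be determined from the documents, and no millilitre figure is claimed. The conclusion rests on two readings of the text: that the randomization day means Day 0, and that the 12-hour fast with after-meal dosing makes the Day 90 spirometry pre-dose. It should be corrected before enrolment, because it concerns both the baseline and the interpretation of a primary endpoint and a missed reading cannot be recovered.

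**What to change.** 1. Reconcile the MCID sentence in STUDY DESIGN AND SAMPLE SIZE with Objectives and Primary Endpoints, so that the threshold refers to the Day 90 trough against the pre-treatment baseline. Do not simply carry 12% and 200 mL across: inclusion criterion c uses the same figures for acute reversibility after salbutamol. Either justify them for a trough change or restate the threshold.
2. In the End of Treatment Visit, state that the spirometry is pre-dose and that time since the last study product is recorded.
3. In the Day 0 visit, replace the review with a pre-dose spirometry measurement, name it as the baseline, and state in inclusion criterion b which visit the randomization day means.

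The cost is rewording plus one spirometry per subject at Day 0 (17 at the planned sample size), which criterion b already requires, and a little more clinic time. Because criterion b also selects on the Day 0 reading, regression to the mean is reduced but not removed. The reason to name Day 0 as the baseline is consistency with the design section, not a smaller bias than the screening value once both readings must qualify.

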# Endpoints

#### **Primary Endpoints**

- Change in mean trough FEV1 expressed as mililitres after 90 days of treatment
- Change in mean ACQ-7 scores after 90 days of treatment
- The threshold for change in ACQ-7 scores that is considered clinically important (MCID) is 0.5.

#### Secondary Endpoints

- Changes in mean FeNO (ppb) after 90 days of treatment
- Change in mean eosinophil count (cells/dL) after 90 days of treatment
- Changes in mean serum immunoglobulin E level (IU/ml) after 90 days of treatment

#### **Study Population**

The target population for this study consists of 10 Patients with uncontrolled asthma aged 18 and above. Each subject will have to fulfil the inclusion criteria listed below. Subjects will not be included in the study if they meet any of the exclusion criteria listed below.

#### **Inclusion Criteria**

All adults aged 18 years and above with a prior documented diagnosis of atopic (Th2driven) asthma by a physician based on Global initiative for Asthma (GINA) 2020 Guidelines whose asthma is uncontrolled on ICS/LABA combination therapy based on the following criteria:

- a) A well documented requirement for regular treatment with a minimum dose of either fluticasone /salmeterol combination therapy or budeosnide/formoterol combination therapy in the 12 months prior to screening with or without maintenance of oral corticosteroids (OCS).
- b) Forced expiratory volume (FEV1) > 50% to <80% predicted normal during the screening phase (3 attempts maximum) and on the randomization day prior to the first dose of IMP.
- c) Reversibility of at least 12% and 200 ml in FEV1 after 200 ug to 400 ug (2 to 4 inhalations) of salbutamol during the screening phase (3 attempts maximum), or documented history of reversibility test that met these criteria within 12 months prior to screening.

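### Entry FEV1 window also gates Day 0, so no baseline for the primary FEV1 change is free of selection; without a control arm, regression to the mean biases it

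*Protocol*

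**What the plan says.** - **Entry window.** Protocol, Inclusion Criteria (b): FEV1 must lie between 50% and 80%, both limits excluded, as a share of "predicted normal during the screening phase (3 attempts maximum) and on the randomization day prior to the first dose of IMP". The trial has no randomization. I read this day as the Day 0 baseline visit, because the Baseline section puts the first dose on the following day.
- **Reversibility.** Criterion (c) asks for "Reversibility of at least 12% and 200 ml in FEV1 after 200 ug to 400 ug (2 to 4 inhalations) of salbutamol", again in up to three attempts, but also accepts a documented result from the previous 12 months.
- **Endpoint.** Primary Endpoints: change in mean trough FEV1 "expressed as mililitres after 90 days of treatment".
- **Baseline.** The only statement of baseline timing is in the sentence on the FEV1 threshold in Study Design and Sample Size: "spirometry obtained at baseline (immediately prior to the start of the treatment").
- **Visits.** Spirometry is measured at screening, once FeNO exceeds 25 ppb, and at the Day 90 visit. The Day 0 list has only a review of spirometry, so the Day 0 reading that criterion (b) needs is not scheduled.
- **Design.** The title gives a single-arm trial. The protocol does not define an attempt or say which screening attempt is carried forward.

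**The concern.** A single FEV1 reading is the patient's usual level plus session-to-session error. If a patient enters only when the reading falls inside a window, the errors among those enrolled no longer average zero. Patients near a limit get in partly because their error pushed them inside it. At Day 90 no such condition applies, so the errors average zero again and the mean moves without any treatment effect.

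In a randomized trial both arms carry the same shift and it cancels. Here it goes straight into a primary endpoint. Because criterion (b) gates the screening reading and the Day 0 reading alike, naming either one as baseline in an analysis plan does not avoid the problem. The rule that creates it is in the eligibility text.

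**Working it through.** The protocol has no figure to reproduce: it states no expected FEV1 change, SD, screened mean or power. All magnitudes below rest on assumptions.

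**Inputs from the protocol:** window 50 to 80% predicted; up to three screening attempts; the same window at Day 0; threshold 200 mL; 17 subjects (Study Design section).

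**Assumptions:** true FEV1 among screened patients has mean 80% predicted (range 70 to 85) and SD 12; reading-to-reading SD is 5 points (range 4 to 7); predicted FEV1 is 2.8 L, so 1 point = 28 mL; no treatment effect; a patient is retested until a reading qualifies, up to three times.

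**Hand check, one attempt, that reading as baseline.**
- Readings have variance 12² + 5² = 169, so SD 13. The share due to error is 25/169 = 0.148.
- Standardized limits: (50 − 80)/13 = −2.308 and (80 − 80)/13 = 0.
- Mean qualifying reading = 80 + 13 × (0.0278 − 0.3989)/(0.5000 − 0.0105) = 80 − 9.86 = 70.14.
- Expected null change = 0.148 × 9.86 = 1.46 points, and 1.46 × 28 = 41 mL.
- With a screened mean of 65 the limits are symmetric, the mean qualifying reading is 65, and the null change is 0.

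**Simulation of the remaining cases** (expected true value minus baseline among those enrolled, same assumptions):

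| Baseline used | Attempts | Null change at screened mean 80% |
|---|---|---|
| Qualifying screening reading, no Day 0 gate | 1 | 41 mL |
| Qualifying screening reading, no Day 0 gate | 3 | 59 mL (13 to 132) |
| Day 0 reading, gated | 1 | 24 mL |
| Day 0 reading, gated | 3 | 32 mL (7 to 79) |
| Mean of all pre-treatment readings, Day 0 gated | 3 | 22 mL |
| Day 0 reading, ungated | 3 | 0 mL |

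The ranges cover screened means of 70 to 85 and reading SDs of 4 to 7.

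**Source of the bias.** With a gated Day 0 baseline, retesting adds 32 − 24 = 8 mL. The other 24 mL comes from the cut-off itself.

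**Dependence on the screened mean.** With a gated Day 0 baseline the null change is 0 at a mean of 65% and about −10 mL at 60%. With the screening baseline it is about −20 mL at 60% and −40 mL at 55%.

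**Effect on a test.** The protocol names no test, so this is only an illustration. It takes a one-sample t test with nominal 2.5% in the direction of gain, n = 17, screened mean 80%, between-patient SD 15, reading SD 4 to 8 and predicted FEV1 3.0 L. The false-positive rate is 6 to 11% with the Day 0 gate and 12 to 24% with the screening baseline. With an unselected baseline it stays at 2.3 to 2.7% in every scenario.

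**The case against.** An FEV1 window confirmed before dosing is an ordinary design choice, and the deeper weakness is the missing control arm, which no baseline definition repairs. That stands. An unselected baseline removes this one artefact and does not make a single-arm change attributable to the product.

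The documents do not support several stronger readings that a reader might infer:

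- **That an inert product must show a gain.** The window has a lower limit as well, and retesting can lift a patient above 50% just as it can bring one below 80%. The sign depends on the screened mean, which the protocol does not give.
- **That the three attempts are the main cause.** Retesting until a reading falls below 80% is a natural reading of the attempt limit, but the text does not say so. Even on that reading it adds only about 8 mL to the gated Day 0 figure.
- **That the Day 0 gate makes matters worse.** It lowers the bias compared with a screening baseline (59 to 32 mL). Its fault is that it leaves no pre-treatment reading free of selection.
- **That reversibility testing raises the figure to about 91 mL (44 to 165).** That requires reversibility to be met in the same session as the qualifying reading. Criterion (c) does not require this, since it accepts a documented history.

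It is also fair to say that all the window-only figures lie below 200 mL. But the endpoint is a mean change in millilitres, and a shift of this kind biases it whether or not it reaches the threshold.

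**Conclusion.** The concern holds conditionally. As written, every reading that could serve as baseline for the primary FEV1 change is selected on its own value, Day 90 is not, and no control arm cancels the difference. If screened patients average above about 65% predicted, the expected result with no effect is a gain; at 65% the window gives none; below it, a loss.

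Under the assumed base case the plan as written, with Day 0 as baseline, gives about 32 mL (7 to 79), roughly one-sixth of the 200 mL threshold. If no Day 0 spirometry is done, as the Baseline visit list suggests, the screening reading becomes the baseline and the figure is about 59 mL (13 to 132). The mechanism follows from the protocol text. The size and sign rest on an assumed screened mean, SDs and predicted FEV1.

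**What to change.** 1. In criterion (b), apply the FEV1 window at screening only.
2. In the Baseline visit list, schedule a pre-dose spirometry on Day 0 in place of the review alone, and reconcile that list with criterion (b) and with the baseline timing in Study Design and Sample Size. Without this step, removing the Day 0 condition would also remove the only eligibility or visit text that calls for a Day 0 FEV1.
3. Define baseline as that Day 0 reading, whatever its value. The expected null change is then 0 mL.

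**Cost.** Wording in three places, and no reading beyond the one criterion (b) already requires. Some enrolled patients will be outside the window on Day 0: about 27% in the base case (0.27 × 17 = 4.6, so 4 or 5 of 17), and roughly 15 to 40% over the assumed range.

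**If the Day 0 gate must stay,** define baseline as the mean of all pre-treatment readings, including attempts that did not qualify. This only reduces the bias, from about 32 to 22 mL in the base case.
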